Do you take tutoring outside of school? (Circle) YES NO

How many hours do you spend outdoors when you leave school?Hs

How many hours per day do you spend reading books or doing homework?
.....Hs

How much time per day do you spend playing with your cell phone or tablet?
.....Hs

ON ANY SATURDAY OR SUNDAY.....

How many hours per day do you spend reading books or doing homework?Hs

How many hours per day do you spend outdoors on a weekend day?Hs

How much time per day do you spend playing with your cell phone or tablet?
.....Hs

PART II EYEGLASS DELIVERY

DATE

PART II. BIS (ATTACHMENT QUESTIONNAIRE)
AT THE MONTH OF DEFOCUS EYEWEAR DELIVERY (TELEPHONE SURVEY)
DATE

Have you worn the glasses at home during this month? YES NO

Have you worn glasses all day this month? YES NO

If you answered "YES" to any of the above, continue with these

In general, do you tolerate them well? YES NO

Have you ever had trouble turning your head to look sideways? YES NO

Out of the seven days of the week, how many days do you not use them?.....

Have you ever had trouble turning your head to look down when reading? YES NO

Have you ever had trouble turning your head to look down when walking? YES NO

PART III

DATE SECOND VISIT AFTER SIX MONTHS.....

EYE DER SPHERICALCILINDRICAL AXIS.....

SPHERIC IZQ EYE.....CILINDRITRIC AXIS.....

AXIAL LENGTH OD..... OI.....

PART III (BIS) SIX MONTH ADHERENCE QUESTIONNAIRE

Have you worn your glasses at home during this month? YES NO

Have you worn glasses all day during this month? YES NO

If you answered "YES" to any of the above continue with these.....

In general, do you tolerate them well?

YES NO

Have you found it difficult to turn your head to look sideways? YES NO

Of the seven days of the week, how many days do you not use them?

Did you have trouble turning your head to look down when reading? YES NO

Have you had trouble turning your head to look down when walking? YES NO

PART IV

DATE THIRD VISIT AT TWELVE MONTHS.....

RIGHT EYE SPHERICALCILINDRICAL AXIS.....

LEFT EYE SPHERICAL.....CYLINDRICALAXIS.....

AXIAL LENGTH OD..... OI.....

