mm diameter ring with the treatment,⁴⁰ the national design that was presented has a uniform +3.50 diopter power zone that alters the visual field by 5% at 10 degrees from the circular shaped fovea,³⁸ as presented at the International Myopia Conference a month ago. As it is known that positive defocus in 30-40 minutes of exposure modifies the axial length (measured with Lenstar) by 10 microns due to changes in the choroidal thickness,⁴² The national design has been tested on 17 volunteer subjects showing a significant change of 11 microns in the axial length of their eyes, suggesting this pilot study (in the process of being published) that the lenses should be effective in halting the progression of myopia, as changes in the choroid are the first event in the retinal message that governs ocular growth.⁴³ This, coupled with the survey that gave a good reading tolerance in 70% of the 17 respondents within a month of wearing them, was presented at the Conference and is in the public domain. Respondents found it difficult to walk around with these lenses because they are like an executive bifocal, but tolerated them well for reading at home, with small lateral movements of the head when reading A4 texts or the computer. It is therefore our intention to do a free field test with such lenses on a larger sample.

POPULATION

Consecutive patients between 8 and 16 years of age who attend the institutions accredited for this study. These institutions will be accredited only if they can perform routine studies for myopia control (refraction exam and optical biometry).

USE OF GLASSES

Once the eyeglass prescription has been written by the ophthalmologist, the enrolled patients will be seen in opticians accredited for this study in close proximity to the

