One month after the delivery of the spectacle, the principal investigator in charge will make a telephone call to the parent of the study subject conducting the tolerance survey and thus verifying adherence to spectacle use. The survey is detailed in the attached medical record and responses will be uploaded into the computerised web-based system that will be developed for this study. The system will automate the alerts for these safety calls with automatic emails sent to the principal investigator in the month of spectacle delivery.

PLAN FOR ANALYSING THE RESULTS

The results of numerical variables shall be expressed as mean and standard deviation or median and interquartile range according to whether they are normally or skewed. Nominal variables will be expressed as absolute frequency and percentage. For the comparison of numerical variables, Student's t-test or Mann Whitney U-test will be used as appropriate. Nominal variables will be compared using the Chi-square test or Fisher's exact test as appropriate. A p-value of $p \leq 0,05$.

HUMAN RESOURCES

[name] and [name] are in charge of the design and control of the research. Statistical analysis will be performed by [name]. Physicians accredited to treat patients will have to demonstrate the ability to perform routine consultations for myopia control, refraction studies under cycloplegia and optical biometry. Once accredited, they will have a username and password to upload their data into the web form. Accredited doctors will be in permanent communication with doctors [name] and [name]. There will be a myopia progression monitoring system within the computerised system that will send reports if any child progresses more than 0.25 dioptres in six months to alert researchers so that precautionary measures can be taken in such cases.

MATERIAL RESOURCES

Optotypes, Retinoscope, Autorefractometer and Biometer posters of accredited institutions.

Approximately four institutions with a high turnover of paediatric consultations are expected to be accredited for an estimated enrolment time of 6 months.

Peripheral defocus spectacles will be provided by the sponsor (NOVAR) free of charge to all study subjects for one calendar year with the possibility of extending the study for two years. At the end of the study, if the expected positive results are found, the glasses will remain in the possession of the study subjects.

FINANCIAL RESOURCES

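### Children who report no wear in the current month skip every tolerance and walking question, and no form shown asks why wear stopped or about falls and complaints

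*Combined protocol and SAP*

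**What the plan says.** PART II. BIS, the telephone survey one month after delivery, opens with two wear questions: "Have you worn the glasses at home during this month? YES NO" and "Have you worn glasses all day this month? YES NO". A family that answers YES is told "to any of the above, continue with these". Five items sit behind that rule: general tolerance ("In general, do you tolerate them well? YES NO"), looking sideways, days per week without the glasses, reading, and walking ("Have you ever had trouble turning your head to look down when walking? YES NO"). PART III (BIS), at six months, repeats the two wear questions, again about the current month, and the same rule. PART IV, at twelve months, as shown holds only refraction and axial length.

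SAFETY PRECAUTIONS makes the one-month survey the safety measure: "The system will automate the alerts for these safety calls". On the 17-subject pilot, DEFOCUS GLASSES OF NATIONAL DESIGN reports: "Respondents found it difficult to walk around with these lenses".

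OBJECTIVES makes tolerance and adherence primary. EVALUATION OF TOLERANCE AND ADHERENCE sets tolerance as GOOD or BAD from the child's answer. It reports adherence as missed scheduled visits relative to all children enrolled and given glasses.

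**The concern.** A child who has given up the glasses is the one whose tolerance answer matters most, and the skip rule can leave that answer uncollected. This is half of the primary objective. If children not asked drop out of the percentage, or stand on an older favourable answer, reported tolerance can be too high.

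The same survey carries the safety monitoring. Difficulty walking is the one problem the pilot already showed, yet the only walking item is a fixed question about turning the head to look down. A fall, an injury or any other complaint has no place on the forms shown. Neither does the reason a child stopped. In a one-year study these answers cannot be recovered afterwards.

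**Working it through.** The plan gives no figure on this point to reproduce, so the main check traces the forms.

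**1. Skip rule by wear history**

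| Wear history | One-month call | Six-month form |
|---|---|---|
| Never worn | Two NOs; all five items skipped | Two NOs; skipped |
| Worn for some days, stopped within the first month | Literal answer YES, all items asked; skipped only if the family takes the question to mean current wear | Two NOs; skipped |
| Worn at one month, stopped before the six-month recall window | Asked | Two NOs; skipped |
| Still wearing | Asked | Asked |

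**2. What is on file for the third row.** The month-1 tolerance answer may be YES. The six-month form shows non-wear and nothing more. PART IV adds no tolerance answer. If the child attends every visit, the visit-based definition counts the child as adherent. EVALUATION OF TOLERANCE AND ADHERENCE does not say which contact supplies the reported tolerance answer, so the month-1 YES can stand as GOOD.

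**3. Harm and reason items.** Items on falls, injuries or other complaints, on the forms shown: 0. Items on why the glasses were not worn or were stopped: 0. The progression alert under HUMAN RESOURCES concerns change in refraction, not complaints.

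**4. Denominator, illustration only**
- N = 50, from SAMPLE AND SAMPLE SIZE.
- 70% GOOD among those asked. This is a placeholder borrowed from the pilot's reading tolerance in 17 volunteers; it is not an estimate for these children.
- k = number skipped, assumed to be 5 to 10. The documents give no such figure.

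If no skipped child counts as GOOD, the share of all 50 is 0.70 × (50 − k)/50.
- k = 0: 35/50 = 70%, no difference.
- k = 5: 0.70 × 45/50 = 31.5/50 = 63%, 7 points lower.
- k = 10: 0.70 × 40/50 = 28/50 = 56%, 14 points lower.

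If instead every skipped child counts as GOOD, the shares are (31.5 + 5)/50 = 73% and (28 + 10)/50 = 76%. The 7 to 14 points are therefore the largest overstatement from the denominator at these assumed shares.

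**5. Standing on an older answer.** This is a separate route. Each child kept as GOOD on a month-1 YES who would later have said NO adds 1/50 = 2 points.

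**The case against.** The strongest objection concerns the one-month call. It falls a month after delivery, so the wear question covers roughly the whole period since the child received the glasses. A child who tried them, had trouble walking and stopped can truthfully say YES and is then asked every item. This stands. A reader might infer that the safety call misses every child who stopped, or that such experiences are never recorded; the form's wording does not support that. Two NOs are themselves a record of non-wear, and missed visits are counted against all children given glasses.

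A reader might also infer that tolerance is by definition calculated among continuing wearers. The plan states no denominator for tolerance at all. That is a gap that permits overstatement; it does not show that overstatement will occur. The 7 to 14 points likewise only restate an assumed number of skipped children.

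On harm, the pilot text reports difficulty walking, not falls. METHODS directs wear mainly to screens and books at home from late afternoon, which would limit exposure while walking. USE OF GLASSES, however, instructs wear for as much time as the child can manage after the first days, and the two passages must be reconciled. There are other contacts too: the optician observes mobility at delivery, and the principal investigator speaks weekly with each centre. No recording form is shown for either. Consent pages are not available, so reporting instructions there cannot be checked.

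Finally, putting every tolerance and walking item to children who never wore the glasses would add meaningless answers and dilute the walking result. That is right, and the fix allows for it.

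What the objection does not answer is the child who stops between the one-month call and the six-month recall window.

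**Conclusion.** The point holds in a limited form. At one month the skip rule omits children who report no wear. At six months it omits all who stopped before that month, and PART IV as shown does not ask again. Such a child can remain GOOD on a month-1 answer and adherent by attendance. The reason for stopping, and any fall, injury or complaint outside the fixed items, is not collected on any form shown, although the one-month survey is the plan's safety call.

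The effect on the primary tolerance percentage cannot be estimated from the documents. Under the assumed 5 to 10 skipped children of 50 and 70% GOOD among those asked, the denominator effect is at most 7 to 14 points, reached only if none of the skipped children counts as GOOD. The fault in the forms does not depend on these figures. The change is a cheap improvement, best made before data collection because the missing answers cannot be rebuilt later.

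**What to change.** **PART II. BIS and PART III (BIS).**
- Keep the two wear questions. After two NOs, ask whether the glasses were worn at all since the last contact, and why they were not worn or were stopped.
- Put the tolerance and walking items to any child who has worn the glasses since the last contact.
- At both contacts, ask every child about any fall, injury or other complaint since the last contact (yes/no, describe).

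**EVALUATION OF TOLERANCE AND ADHERENCE.**
- State that tolerance is reported over all children given glasses.
- Count a child who stopped because of the glasses as BAD.
- Show never-wearers and children not asked as a separate category, with a sensitivity result that counts them as BAD.
- Tabulate falls and complaints over all children given glasses.

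**Cost.** Two or three short items and a changed skip rule, in a web system that SAFETY PRECAUTIONS describes as still to be developed. The tolerance figure may turn out less favourable.

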ophthalmology offices that are members of the research team. The opticians and ophthalmologists will be asked to watch a video on myopia control developed by the principal investigators where this treatment methodology is explained during the evaluation process at the center of care. The opticians will verify the optical centration in the frames chosen ad hoc, with a modern digital centration system provided by the sponsors. After 15 days, when the glasses with the correct centering are ready, the subjects will go to the optician's office to try on the glasses in that room. On this occasion, as always in these cases, the optician will evaluate the subject's adaptation and mobility in the optician's shop, instructing the child to wear the glasses at home for a couple of days and then to wear them for as long as possible.

SAMPLE AND SAMPLE SIZE

The sample size will be 50 subjects of both genders to compare with the studies abroad that consist of an n between 40 and 90 subjects and the natural history in our country that counted 114 subjects. There will be a group of subjects who will be treated with the nationally designed defocus glasses. Statistical calculation for a difference of 0.25 diopters in progression with respect to controls, for a standard deviation of 0.50 diopters gives an $n = 31$ subjects and taking into account a 20% loss to follow-up the n should equal 38 subjects in the group. Thus reaching 50 subjects exceeds expectations.

METHODS

This field study to test tolerance and percentage of effectiveness of defocus lenses in the control of myopia will include boys and girls from 8 to 15 years of age who voluntarily

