Adherence will be evaluated at the one-year follow-up and will be reported as the number of cases that failed to complete the three scheduled visits in one year with respect to the total number of cases that were enrolled in compliance with the first visit and the delivery of the spectacle. Tolerance of these glasses will be assessed with a tolerance questionnaire that is presented in the attached medical record. This questionnaire has already been tested on 24 subjects aged 18 to 24 years in a pilot trial presented at the International Myopia Conference, as explained in the previous section on the defocus spectacle, showing good tolerance in these subjects. Some tests in younger children that were performed in the last months show that tolerance is very good in them, since minors have greater plasticity and adaptability than young adults previously tested. Tolerance and adherence will be classified as GOOD / BAD, in a dichotomous way, with the cut-off according to the answer given by whether the child tolerated them well or not. On the other hand, tolerance will also be evaluated in dichotomous form with responses to reading and walking

performance.

PROCEDURES TO GUARANTEE ETHICAL ASPECTS

The anonymity of all participants will be preserved. Patients' names will be removed from the database for statistical analysis. The only ones who will know the names of the patients are the physicians involved in their primary care, and they will have to keep the information in their respective institutional medical records and enter the data necessary for the research in a web form designed by the sponsoring company.

The Declaration of Helsinki and its modifications, the Good Clinical Practices guide, the harmonization norms and the resolution of the Ministry of Health 1480/11 will be observed and taken into account as guidelines (See informed consent ANNEX VI). It is stated for the record that the principal investigator does not have any type of conflict of interest since the patenting of the defocus glasses is the responsibility of the sponsor's company.

SAFETY PRECAUTIONS

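### The reading and walking tolerance items ask about any trouble 'ever' at one month, drop that word at six months and set no recall window, so early and current trouble cannot be separated

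*Combined protocol and SAP*

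**What the plan says.** The primary objective (Objectives) is tolerance of, and adherence to, the glasses. Evaluation of Tolerance and Adherence sets the main GOOD/BAD split by the answer on whether the child tolerated the glasses well. It then adds that "tolerance will also be evaluated in dichotomous form with responses to reading and walking" performance. It names no time point for these two measures and does not mention the sideways item.

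The questionnaire is printed twice, as Part II Bis (telephone survey at one month) and Part III Bis (six months). The head-turning items read:

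| Item | One month | Six months |
|---|---|---|
| Reading | "Have you ever had trouble turning your head to look down when reading" | "Did you have trouble turning your head to look down when reading" |
| Walking | "Have you ever had trouble turning your head to look down when walking" | "Have you had trouble turning your head to look down when walking" |
| Sideways | "Have you ever had trouble turning your head to look sideways" | "Have you found it difficult to turn your head to look sideways" |

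The general tolerance item is in the present tense and has the same wording on both forms. The wear items on both forms refer to the current month; the head-turning items carry no such window.

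Use of Glasses describes a start-up phase: the optician assesses adaptation, "instructing the child to wear the glasses at home for a couple of days", and wear is extended after that.

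**The concern.** The plan gives reason to expect trouble that passes. It describes a short initial period at home, it reports under Defocus Glasses of National Design that pilot wearers had difficulty walking, and it argues under Evaluation of Tolerance and Adherence that children adapt better than the young adults tested before. A child who struggles on the first days and then adapts is the outcome the investigators hope for. On the one-month form that child's truthful answer to the reading or walking item is YES, the same answer as that of a child who still cannot manage.

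Two things are at stake. The one-month reading and walking tolerance rates may be lower than current tolerance. And if someone sets the two forms side by side to show adaptation, the change in the question is mixed with any change in the children. There is one treated group and the virtual control group supplies progression data only, so no comparison arm answers the same items and cancels a wording effect.

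**Working it through.** The plan states no figure on this point, so there is none to reproduce. The check is a comparison of the texts, followed by an illustration on assumed values.

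**Step 1: what each answer can mean.** At one month, *ever* is bounded in practice by the delivery date, so the item covers about a month of wear, including the first days. At six months the item can be read in two ways:

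- As recent experience, following the month named in the wear items. Trouble confined to the first days is then YES at one month and NO at six months, and an apparent fall appears without any change in current tolerance.
- As everything since delivery. Early trouble is then YES on both forms. There is no wording effect between them, but neither form measures current status.

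Under neither reading do both forms measure current tolerance, and the plan does not say which is meant.

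**Step 2: which measures are touched.** The main GOOD/BAD split uses the general item, which has no *ever* and does not change, so it is untouched. The reading and walking measures are touched. The sideways item has the largest change of wording, since its stem changes too, but it is outside the stated tolerance definition.

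**Step 3: effect on the one-month rate (illustrative).** Let t be the share of children with early trouble only; the documents do not give it. Taking YES to trouble as the unfavourable answer, which the plan implies but does not spell out:

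one-month tolerant rate = current tolerant rate − t

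With the planned 50 subjects (Sample and Sample Size), 5/50 = 10 points for each 5 such children. If current tolerance is assumed to be 80%, then t = 20% gives 80 − 20 = 60%, and t = 40% gives 80 − 40 = 40%.

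**Step 4: effect on a one- to six-month comparison (illustrative).** Assume that all 50 answer both forms, that persistent trouble is the same at both times, and that every child with early trouble only answers NO at six months. The number who switch is x = 50t, all in one direction, so the exact McNemar p = 2 × 0.5^x. The Fisher columns treat the two time points as unpaired, for persistent trouble of 10% (5 children) and 30% (15 children).

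| t | x | McNemar p | Fisher p, 10% persistent | Fisher p, 30% persistent |
|---|---|---|---|---|
| 10% | 5 | 0.063 | 0.26 | 0.40 |
| 12% | 6 | 0.031 | 0.17 | 0.30 |
| 20% | 10 | 0.002 | 0.023 | 0.066 |
| 30% | 15 | <0.001 | 0.001 | 0.005 |

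So 6 children out of 50 would be enough to cross the plan's 0.05 threshold in a paired test with no true change. The unpaired test, the kind the plan lists, needs more. These figures show that the effect could matter, not that it will occur.

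**The case against.** The strongest reply is that the primary tolerance result is largely protected. That stands: a child with trouble only at the start can answer that the glasses are well tolerated and is classed GOOD. A reader might infer from the *ever* wording that first-days trouble makes a child intolerant in the main classification; the protocol does not support this.

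A reader might also infer that any improvement from one to six months is bound to be partly a wording effect. The documents do not support that either. Plan for Analysing the Results describes no such comparison, and families may read the open six-month items as covering the whole period. Only *could be* is justified.

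The English text is visibly a translation, and other parallel items differ slightly for no apparent reason. The forms given to families may not differ by *ever* at all. This calls for a check of the source-language forms; it does not remove the discrepancy from the document under review, and it would not supply the missing window.

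Finally, recording any early difficulty is reasonable for a call that the protocol places under Safety Precautions. That is true, but it is a different purpose from scoring tolerance, and a separate item would serve it.

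**Conclusion.** The concern holds in limited form. The reading and walking items are not equivalent at one and six months and share no recall window. The one-month answers cannot separate trouble in the first days from current intolerance, so the one-month rates on these two additional measures may be understated, and a difference between the forms could partly reflect wording. The main GOOD/BAD classification is unaffected.

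The size is unknown. The figures above rest on an assumed current tolerance of 80%, assumed shares with early trouble only of 10% to 40%, and, for the comparison over time, families answering NO at six months about early trouble. The plan does not establish any of these. The change is still worth making before data collection, because a YES to *ever* cannot be split afterwards into early and current trouble.

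**What to change.** 1. Check the source-language forms to see whether the difference exists there.
2. Give the reading and walking items one identical wording with one explicit recall window on both forms. The last 7 days is one possible choice; using the same window twice matters more than its length. Harmonise the sideways item as well, for consistency.
3. State in Evaluation of Tolerance and Adherence which time point defines reading and walking tolerance, and which answer counts as unfavourable.
4. If early trouble is of interest, record it in a separate item about the first days and keep it out of the dichotomy.

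The cost is rewording three items on two forms, easiest before the web form is programmed, and a short addition to the tolerance section. The downside is slightly reduced comparability with the questionnaire as piloted in 24 young adults.

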Given the above-mentioned background, the following study has been designed to evaluate the arrest of myopia progression with the daily use of nationally designed glasses, comparing such progression with a virtual control group of similar age in a population of myopic children and adolescents of the same environment in our country.

WORKING HYPOTHESIS

The nationally designed lenses can be as effective as the proven international industry designs that have been subjected to controlled trials against natural history of the disease.

PURPOSE

To treat a group of consecutive volunteer patients who choose between the affordable treatment in our environment (daily diluted atropine drops for several years) or the special lenses for myopia control designed by the National Industry. The purpose is to compare the progression during one year with the national lenses with respect to the progression with the foreign lenses and/or with the natural history of a virtual control group.

OBJECTIVES

Primary

To assess whether the intervention with locally designed spectacles is well tolerated and adhered to with daily use in childhood and adolescence.

Secondarily

To assess whether intervention with locally designed glasses can control myopia progression in childhood and adolescence.

DEFOCUS GLASSES OF NATIONAL DESIGN

The design of the national defocus lens is based on the original design presented by Carly Lam,⁴⁰ with a 9 mm central zone for distance correction and a correction ring with a +3.50 dioptre defocus between 9 and 32 mm in diameter to act in principle on the para foveal zone which is the one that detects the defocus that governs the growth of the eye.⁴¹ Instead of peripheral defocusing micro lenses that do not alter the visual field in the area of the 32

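### No wear or tolerance question appears at 12 months in the text provided, and one-year adherence is defined by visit attendance rather than by the daily use named in the primary objective

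*Combined protocol and SAP*

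**What the plan says.** The primary objective (Objectives) is "To assess whether the intervention with locally designed spectacles is well tolerated and adhered to with daily use in childhood and adolescence". It gives no time point.

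Evaluation of Tolerance and Adherence then sets three rules:

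- Visit measure: "Adherence will be evaluated at the one-year follow-up and will be reported as the number of cases that failed to complete the three scheduled visits", relative to all children enrolled who made the first visit and received the glasses.
- Tolerance instrument: "Tolerance of these glasses will be assessed with a tolerance questionnaire that is presented in the attached medical record". The section does not say when it is given.
- Dichotomy: "Tolerance and adherence will be classified as GOOD / BAD, in a dichotomous way, with the cut-off according to the answer given" on whether the child tolerated the glasses well. No time point is named here either.

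The record form at the end of the protocol has a questionnaire in Part II BIS (telephone, one month after delivery) and again under "PART III (BIS) SIX MONTH ADHERENCE QUESTIONNAIRE". Part IV, which opens with "DATE THIRD VISIT AT TWELVE MONTHS", has lines for refraction and axial length. The text ends there.

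**The concern.** The one adherence measure tied to one year counts attendance. The objective is about daily use, and Methods tells children to wear the glasses every day from late afternoon until bedtime. A child can attend all three visits without wearing them.

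Two results are at stake. The adherence figure for the primary objective may be too favourable, because a child who stopped wearing the glasses but kept attending is counted as a success. The secondary objective, one-year progression, also becomes hard to read: a weak result could mean an ineffective lens or a lens left in a drawer after month 6, and the data could not separate the two. Lasting wear should not be taken for granted. The pilot described under Defocus Glasses of National Design reports good reading tolerance in 70% of 17 respondents within a month, and difficulty walking in the lenses.

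**Working it through.** No figure in the plan needs reproducing; the check is a comparison of sections.

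**Step 1. Items by time point (record form).**

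| Item | Month 1 (Part II BIS) | Month 6 (Part III BIS) | Month 12 (Part IV) |
|---|---|---|---|
| Worn at home; worn all day (2 items) | yes | yes | none |
| Days per week not used (1 item) | yes | yes | none |
| Tolerated in general; three head-turning items (4 items) | yes | yes | none |
| Refraction, axial length | not applicable | yes (Part III) | yes |

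Each questionnaire has 2 + 1 + 4 = 7 items.

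**Step 2. Other sources of wear data.** Methods and Safety Precautions describe one telephone survey, one month after delivery. Methods mentions monitoring devices, but only as likely, only in a selected group, and only for surveyed habits such as reading and time outdoors. Exclusion and Elimination Criteria judges poor adherence by missed follow-up interviews, which is attendance again. None of these measures spectacle wear after month 6.

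**Step 3. Which rule uses which data.** The visit measure uses attendance at baseline, month 6 and month 12, and no questionnaire answer. The GOOD/BAD class uses the tolerance answer, which exists only for months 1 and 6. Days not used per week, the item closest to daily use, enters neither rule.

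**Step 4. Period without data.** Months 7 to 12 are 6 of 12 months, so 6/12 = 50% of follow-up has no wear or tolerance record.

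**Step 5. Recall windows.** Only the worn-at-home and worn-all-day items are limited to the current month. For those two, coverage is at most 2/12 = 17% of the year. Repeating them unchanged at month 12 gives 3/12 = 25% and leaves months 7 to 11 uncovered. The other five items state no window.

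**Step 6. Sensitivity of the visit measure.** Taking the 50 subjects in Sample and Sample Size as the denominator (an assumption), each child who stops wearing the glasses but attends moves the adherence percentage by 1/50 = 2 percentage points. The documents give no basis for estimating how many such children there will be.

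**Step 7. Skip instruction.** In both questionnaires the remaining five items follow only if at least one of the two wear items is answered yes. A child who answers no to both gives no days-not-used and no tolerance answer, and so has no answer from which to assign GOOD or BAD.

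**The case against.** **The page may simply be missing from the text.** In Part III the questionnaire follows directly after the axial-length line, and the text stops at that same line in Part IV, so a lost page would look just like this. Annexes I and VI are cited but not shown. The silence of the protocol body is weak evidence, since it does not describe the six-month questionnaire either, yet that one exists. This stands: absence is not proven. It does not rescue the visit measure, which ignores questionnaire answers whatever pages exist.

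**A one-year adherence measure does exist.** A reader might infer that the one-year result rests on month 1 and month 6 answers alone. The documents do not support that: visit completion is a 12-month measure, and the objective carries no time frame of its own. One year comes from the adherence section and the study period. The fault is that this measure captures retention.

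**Wear is not unknown for ten months out of twelve.** A reader might infer from the 2-of-12 count that the whole instrument covers only two months. That holds for two yes/no items. The month 6 answers on days not used and general tolerance may reflect a longer period.

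**A 12-month page alone would not settle the matter.** Correct. Repeating the items unchanged would detect a child who had stopped by month 12 but not show when, and would still leave open which answer defines GOOD/BAD.

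**Conclusion.** The point holds in this form. In the text provided, no wear or tolerance item is recorded or planned after month 6. The visit measure counts as adherent any child who stops wearing the glasses but keeps attending. The GOOD/BAD class has no 12-month answer to draw on and no named time point. Half of the follow-up therefore has no wear record against which to set 12-month progression.

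The missing-page part assumes that the record form is complete as shown, so confidence in it is moderate. The finding that attendance stands in for daily use does not depend on that assumption. The documents do not show that the adherence figure will be wrong by any particular amount, nor that the primary objective cannot be addressed at all: month 1 and month 6 data will exist.

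**What to change.** - Add a Part IV (BIS) at the existing 12-month visit with the Part III (BIS) items. Ask the wear and days-not-used items of every child, without the skip.
- Add wording that covers the period since the six-month visit: usual days per week not used, and whether and in which month wear stopped.
- Define one-year adherence from reported days not used per week at months 1, 6 and 12, with any cut-off fixed before the data are examined.
- State that the 12-month answer gives the one-year GOOD/BAD class, and how children without one are counted.
- Report completion of the three visits separately, as retention.

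The cost is one extra page and a few minutes at a visit already planned. The answers rest on recall, and the adherence figure may be less favourable than visit completion. If a 12-month questionnaire already exists, check it for the wording on wear since month 6 and for the skip; the changes to the definitions are still needed.
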